Mixed methods analyses will be used to evaluate the following three aims:

1. *To compare the effectiveness of two implementation strategies (LEAP Quality Improvement Learning Program + Academic Detailing (AD) vs. AD alone) on potentially inappropriate medication use, using a pooled analysis of effects across three trials at 18 months, two years, and three years post-baseline at the clinic-level, based on monthly assessed data from 13-36 months;*
2. *To compare the effectiveness of the two implementation strategies on secondary outcomes specific to each trial at 18 months, two years, and three years post-baseline, based on monthly assessed data from 13 to 36 months; and*
3. *To explore the effects of implementation, provider behaviors and experiences, and context, on sustained improvements in potentially inappropriate medication use.*

Methods

Clinic Randomization

Within each trial, clinics will be randomized after assenting to participate (equivalent to enrollment). Clinics will be assigned to one of two arms by a statistician, stratified further by clinic type (medical center, community clinic, or Community Living Center) if needed to ensure partial balance between arms with respect to potential confounders associated with culture and complexities associated with clinic location [1,2].

Outcomes and Analyses

As part of a pooled analysis, we will compare the same two implementation strategies across all three EBPs and take a unified approach to implementation and evaluation across the trials. Table 1 shows MIDAS measures, data collection timeframe, and data sources. While a unified dichotomous outcome, i.e., potentially inappropriate medications, was identified for each trial to allow for the pooled analysis, each trial will also be analyzed individually (see Table 1).

Table 1: MIDAS Measures showing Data Sources and Timepoints by Aim

Aim	Type	Source
Aim 1: Primary outcome		
Service Outcomes		
Proportion of potentially inappropriate care	Quantitative	CDW administrative data
Aim 2: Secondary outcomes		
Service Outcomes		
VIONE Trial		
Potentially inappropriate use of proton pump inhibitors (PPIs), aspirin, and CNS active medications (e.g., muscle relaxants), analyzed one at a time	Quantitative	CDW administrative data
Monthly medication costs for all drugs	Quantitative	CDW administrative data
Number of pharmacist medication reviews	Quantitative	CDW administrative data

Aim	Type	Source
DOAC Trial		

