If we find notable baseline demographic difference between arms within trials, we will use a generalized linear mixed model (GLMM) with logit link to estimate the between-arm difference while adjusting for baseline age, sex, and race difference with monthly person level response (yes/no) data from post-implementation period of months 13 to 36. In addition to time, AD+LEAP indicator and trial type indicators as predictors, the GLMM model using patient level data will include patient age, sex, race, and random intercepts for patients nested within clinic to adjust for potential correlation within clinics and serial correlation over time. The parameter estimate for the LEAP+AD arm indicator will be used to estimate the time-averaged odds of inappropriate medication use during the post-implementation period for patients in clinics randomized to LEAP+AD compared to the odds of the same patients if their clinics were randomized to AD. Although the GEE and GLMM models give different summary estimates with different interpretations, the GLMM model allows for adjusting for patient characteristics, and a consistent substantive conclusion will assure us of the evidence for the effect of LEAP when added to AD. Similar to the GEE model, we will test if the odds ratio of LEAP+AD vs. AD changes over time by including time by arm interaction term, and if the interaction term is significant, we will obtain adjusted ORs associated with LEAP+AD compared to AD at 18 months, 2-years, and 3-years.

For each trial we will also compare AD and AD+LEAP to usual care controls. To do this, we will perform a non-randomized secondary analysis for each trial. The analysis will have the same primary outcome variable and use the same generalized linear mixed model (GLMM) with logit link. The primary control group will be all non-participating sites. We will also use a secondary analysis, where for each intervention site we will have two control sites that are matched on clinic size (within 50%), pre-intervention outcome rate (within 30 rankings of all sites), and region of the country. These analyses will adjust for the clinic-level variables clinic size, intervention outcome rate, region of the country and the patient-level variables age, sex, and race.

Aim 2: Secondary Outcomes and Analyses

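### The usual-care comparison uses post-implementation months only and allows for no prior trend, so a trend at assenting sites that already differed from control sites could be mistaken for an effect of AD or AD+LEAP

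*Combined protocol and SAP*

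**What the plan says.** The usual-care comparison is in the last paragraph of the Aim 1 section of the combined protocol and SAP. The plan is open about its status: "we will perform a non-randomized secondary analysis for each trial". On the model it says: "The analysis will have the same primary outcome variable and use the same generalized linear mixed model (GLMM) with logit link". The preceding paragraph defines that GLMM on "monthly person level response (yes/no) data from post-implementation period of months 13 to 36". Its terms are listed there, beginning "In addition to time, AD+LEAP indicator and trial type indicators as predictors", followed by patient age, sex and race and random intercepts for patients within clinic.

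On controls: "The primary control group will be all non-participating sites". A further analysis takes two controls per site, matched on clinic size, "pre-intervention outcome rate (within 30 rankings of all sites), and region of the country". On covariates: "These analyses will adjust for the clinic-level variables clinic size, intervention outcome rate, region of the country", plus patient age, sex and race.

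On how sites enter, Clinic Randomization says "clinics will be randomized after assenting to participate (equivalent to enrollment". Randomisation then divides the assenting clinics between two arms that both contain AD.

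The cover note says that data were collected through 18 months, not 36. It also says that the comparison between arms now adjusts for the pre-period level of inappropriate medication use. It adds no trend term and does not mention the usual-care analysis.

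**The concern.** Both randomised arms receive AD, so this is the plan's only evidence on whether AD, with or without LEAP, improves on usual care. Sites are in the active groups because they agreed to take part, and such sites may differ from the rest in direction of travel as well as in level.

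One term for the outcome rate can equalise level but not slope. Two sites with the same prior rate and different prior slopes drift apart by months 13-18 with no intervention at all. A group-by-time term within the post-implementation window would not help, because there a continuing prior trend looks the same as a growing effect. Matching on the rate leaves slope unmatched too. Nowhere does the plan describe a pre/post contrast, a check for parallel trends or matching on trend. A steeper prior decline at participating sites would flatter AD and AD+LEAP; a shallower one would hide a real benefit.

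**Working it through.** The plan states no trend, event rate, site number or power for this comparison, so it has no figure to reproduce. The check is of the mechanism.

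**Inputs from the documents.** Post-implementation window: months 13-36 as planned (centre 24.5), or 13-18 under the cover note (centre 15.5).

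**Assumptions.** True effect zero; prior trends linear and continuing; differential slope d of 0.02, 0.05 or 0.10 pp per month. The plan does not say over what period the prior rate is measured, so two cases are shown: level at baseline (month 0), and a 12-month average over months -11 to 0 (centre -5.5).

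**Formula.** False difference = d × (centre of post window − centre of pre window).

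Gaps for months 13-18: 15.5 − 0 = 15.5, or 15.5 + 5.5 = 21. For months 13-36: 24.5 − 0 = 24.5, or 24.5 + 5.5 = 30.

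| d (pp/month) | 13-18, baseline level | 13-18, 12-month average | 13-36, baseline level | 13-36, 12-month average |
|---|---|---|---|---|
| 0.02 | 0.31 | 0.42 | 0.49 | 0.60 |
| 0.05 | 0.78 | 1.05 | 1.23 | 1.50 |
| 0.10 | 1.55 | 2.10 | 2.45 | 3.00 |

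**Simulation on the odds-ratio scale.** A logit GEE clustered by clinic stood in for the GLMM, with 200 runs per setting. All settings are assumed: 10 participating and 100 control sites, 400 patients per clinic-month, prior level 30%, pre-period months -12 to -1 (centre -6.5). The post-only model had group, time and pre-period level. The alternative used pre and post months with group-specific trends.

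| Trend, pp/month (no true effect) | Post-only OR, 13-18 | Post-only OR, 13-36 | Pre-trend OR, 13-18 | Pre-trend OR, 13-36 |
|---|---|---|---|---|
| None | 1.00 | 1.00 | 1.00 | 1.00 |
| −0.2 at all sites | 1.00 | 1.00 | 1.01 | 1.00 |
| −0.1 extra at participating sites | 0.90 | 0.86 | 1.01 | 1.00 |
| −0.2 extra at participating sites | 0.81 | 0.75 | 1.01 | 1.01 |

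Hand check of the 0.90: the gap is 15.5 + 6.5 = 22 months; 0.1 × 22 = 2.2 pp; 30% becomes 27.8%; OR = (0.278/0.722)/(0.300/0.700) = 0.90.

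Only the odds ratios should be read from this. With 10 participating clusters, the post-only model rejected in 10-12% of runs even with no differential trend. The pre-trend model's lack of bias is built in, because the data were generated with linear trends that continue.

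**Price of the pre-trend model.** Take independent monthly noise with variance s² per site and a slope estimated from 12 pre-months, whose sum of squares about their mean is 12 × (12² − 1)/12 = 143. For months 13-18 a simple change from the pre-period mean has variance s²(1/6 + 1/12) = 0.25s². Extrapolating the pre-trend over 21 months adds s² × 21²/143 = 3.08s², giving 3.33s². The SD ratio is √(3.33/0.25) = 3.7. A simulation with 20 and 120 sites and no slope differences between sites gave ratios of 1.9 to 3.6 at months 13-18 as the autocorrelation fell from 0.95 to 0. Real slope differences between sites would narrow the gap.

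**The case against.** The plan itself calls this analysis non-randomised and secondary, and adds a matched version. The primary aim, LEAP+AD against AD, is protected by randomisation. Both points stand and limit the weight of the concern.

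A reader might infer that participating sites were already improving faster, so that any benefit over usual care will be overstated. The documents do not support that. They say only that clinics assent, not why, and they contain no trend data. Clinics might equally join because they were doing worse. A decline across the whole health system, shared with the controls, does no harm.

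A reader might also infer that the large control pool would give a false result a deceptively narrow interval. That does not follow, because the participating sites limit precision. With 20 of them (assumed), √(1/20 + 1/40) = 0.274 for 2:1 matching and √(1/20 + 1/120) = 0.242 for 120 controls, a reduction of about 12%.

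Two textual points also count. The post-only window is inherited through the reference to the same model and is not restated for usual care. And the cover note replaces the patient-level model for the comparison between arms, so whether the usual-care GLMM was kept is not stated. Neither supplies the missing trend term: the revised model also adjusts for level only.

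Finally, the remedy rests on a strong assumption and can be much less precise, as the working shows. That argues against making it a condition for claiming an effect, but not against reporting it.

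**Conclusion.** The gap is real, in a limited form. As written, the usual-care comparison cannot separate an effect of AD or AD+LEAP from a prior difference in trend between assenting and control sites. Its direction and size are unknown. If the differential slope were 0.05 pp per month, the false difference at months 13-18 would be about 0.8 pp (level at baseline) to 1.0 pp (12-month average). These figures rest on an assumed slope, an assumed pre-period and linear continuation of trends, and one slope in percentage points need not suit three outcomes with different denominators.

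The covariate list adds an ambiguity: it names the outcome rate without the prefix that the matching sentence uses. The matching sentence supports reading it as the pre-intervention rate. Taken literally, it would be a rate measured during the intervention, which would leave the all-sites analysis with no adjustment for prior level and would condition on a post-baseline variable.

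Nothing here bears on the randomised LEAP+AD versus AD comparison, and the point should not be read as a criticism of it.

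**What to change.** 1. Extract pre-baseline monthly data from the same administrative source, for example 12 months, for participating and control sites. Align both groups on calendar months, since control sites have no baseline date of their own.
2. Report the difference in pre-period slope between participating and control sites, with its interval, for each trial.
3. Add a comparative interrupted time series with group-specific pre-trends as a sensitivity analysis beside the planned model. State any disagreement between the two when interpreting an effect over usual care. Agreement should not be a required condition for claiming one.
4. Correct the covariate to the pre-intervention outcome rate, and define the period over which it is measured.
5. State which model and which follow-up window apply to the usual-care comparison after the changes in the cover note.

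The cost is a further extraction of data of a kind already in use, one added model per trial, and some wording. No new contact with sites is needed. The added model assumes that prior trends would have continued linearly, and it may be considerably less precise than the planned one. Because the cover note describes data collection as finished, the addition should be labelled post hoc.

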MAINTAINING IMPLEMENTATION
THROUGH DYNAMIC ADAPTATIONS

MIDAS Quality Enhancement Research Initiative

Center for Clinical Management Research

[name]

[name]

[contact]

Official Title of Project: MIDAS Cluster Randomized Controlled Trial of Implementation Strategies to Optimize Use of Medications in VA Clinical Settings (MIDAS cRCT)

ClinicalTrials.gov ID: NCT05065502

Date: 09/24/2025

Please find the Study Protocol and Statistical Analysis Plan below. Since the creation of this document, the following changes have been made to the analysis plan:

- Data was collected through 18 months post-baseline rather than through 36 months due to time constraints.
- Instead of a patient-level dichotomous response over time, the differences between arms were modelled as a single outcome adjusting for the evidence-based practice (EBP) and the level of potentially inappropriate medications (PIMs) in the pre-period to address the large difference in PIMs between EBPs.
- After conducting additional testing of our algorithm for detecting CBTI sessions, we found the algorithm to be adequately sensitive to detecting *any* CBTI but not accurate for detecting the number of CBTI sessions (e.g., CBTI could often be mentioned in the context of a referral or some other ongoing treatment). Thus, the secondary outcome “Change in Mean Cognitive Behavioral Therapy for Insomnia (CBTI) Sessions Completed” could not be analyzed.
- We had originally planned for all CBTI sites to provide information regarding where in the medical records we could identify referrals. However, prior to launching the trial, we determined several of the sites' processes for referrals were not distinguishable as referrals vs. other forms of communication (e.g., adding a therapist as a cosigner to a note), making collection of this data impractical. Thus, we did not have sites collect referral criteria and the secondary outcome “Change in the Monthly Percentage of Patients Referred to Cognitive Behavioral Therapy for Insomnia (CBTI) Across Facilities” could not be analyzed.

A protocol paper for this project, titled “Maintaining Implementation through Dynamic Adaptations (MIDAS): protocol for a cluster-randomized trial of implementation strategies to optimize and sustain use of evidence-based practices in Veteran Health Administration (VHA) patients,” was published in May 2022.

[name], MS
Principal Investigator

Aims

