Secondary outcomes for VIONE will be the prevalence of potentially inappropriate use of PPIs; the prevalence of potentially inappropriate use of aspirin; and the prevalence of potentially inappropriate use of CNS active medications (muscle relaxants, anti-psychotics, Z-drugs, and

benzodiazepines) or anticholinergic drugs; number of inappropriate medications at a patient level; monthly medication costs for all drugs, without regard to appropriateness; and number of pharmacist medication reviews.

Secondary outcomes for the DOAC trial will be the sub-components of the “flags” on the dashboard. These include potential mis-dosing, potential medication interactions, or concern for nonadherence. This follows the organizational structure of both the presentation of the flags on the dashboard and the key messages provided to the academic detailing and LEAP teams. Process outcomes will be how often the provider uses the dashboard and rates of new DOAC starts compared to warfarin starts. These outcomes will be kept in alignment with our other work using the dashboard [4].

In stand-alone analyses of the CBTI trial, the primary outcome will be the prevalence of any CBTI receipt among primary care patients actively following with the clinic who are not in hospice/palliative care.

Analyses of secondary outcomes such as percent of potentially inappropriate use of PPI or mean number of CBTI sessions at each clinic month will be similar to that of the primary outcome using the GEE model accounting for correlation over time. We will also conduct separate analyses by trial with the dependent variables that are unique to each trial. For example, for the polypharmacy trial, secondary outcome of interest is count of medications flagged as inappropriate based on Beers’ criteria [3]. We will compare monthly rates of Beers’ list medication use between implementation strategies using generalized linear mixed models with log link.

Aim 3: Exploration of Potential Predictors of Clinical Outcomes

Our process evaluation will follow a multi-phase concurrent nested mixed methods design [5]. This design has three purposes: 1) help prepare all stakeholders and participants prior to the start of each trial; 2) monitor progress of implementation; and 3) explain summative findings. Overall priority is placed on quantitative methods that guide the trials, while qualitative methods are embedded or “nested” within conduct of the trials.

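### The Aim 2 models name no pre-period level of the outcome analysed, and the plan does not say whether the added pre-period PIM term carries over: a cheap gain in precision may be missed

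*Combined protocol and SAP*

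**What the plan says.** Aim 2, in the Aims section, compares the arms at 18 months, two years and "three years post-baseline, based on monthly assessed data from 13 to 36 months". By the cover note, data collection ended at 18 months, which leaves at most months 13 to 18.

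The section on Aim 2 outcomes and analyses says that the secondary analyses "will be similar to that of the primary outcome using the GEE model accounting for correlation over time". The GEE it refers to, under Aim 1, has the post-implementation clinic-month percentage as its dependent variable. Its terms are trial indicators, follow-up time, arm, and time by arm. The count of flagged medications is sent instead to a log-link generalized linear mixed model, for which no covariate is named. The section adds: "We will also conduct separate analyses by trial with the dependent variables that are unique to each trial".

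The only pre-period term in a randomized comparison is in the cover note, which reports that arm differences were "modelled as a single outcome adjusting for the evidence-based practice (EBP) and the level of potentially inappropriate medications (PIMs) in the pre-period", and that this was done "to address the large difference in PIMs between EBPs". The note does not mention Aim 2 in this connection. The one other pre-period outcome term is in the non-randomized usual-care comparison of the primary outcome.

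**The concern.** A clinic's own earlier level is often the best single predictor of its later level. Each Aim 2 outcome also rests on the clinics of one trial, so precision is scarcer than in the pooled analysis. For the insomnia trial the outcome is not minor: "In stand-alone analyses of the CBTI trial, the primary outcome will be the prevalence of any CBTI receipt".

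Two things are unclear. First, the reason given for the pre-period PIM term concerns differences between practices in a pooled model, and that reason does not arise within a single trial. A reader cannot tell whether the term was kept there. Second, even if it was kept, PIM level is not the baseline of every Aim 2 outcome. The VIONE list includes "monthly medication costs for all drugs, without regard to appropriateness; and number of pharmacist medication reviews", and the insomnia trial has any CBTI receipt. For these, an inherited PIM term could use a degree of freedom and return little.

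At stake are wider intervals and lower power than the available data might allow. Validity is not at stake.

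**Working it through.** **Inputs.** The documents give no clinic count, between-clinic SD or pre/post correlation, so there is no stated figure to reproduce. All values below are assumed: N clinics in one trial (12 or 24, allocated 1:1) and a clinic-level pre/post correlation r of 0.3 to 0.8.

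**Step 1: own pre-period level against none.** On clinic means, adjustment multiplies the residual variance by 1 − r². It also costs one degree of freedom and allows for chance imbalance in the covariate. The ratio of 95% CI widths, adjusted to unadjusted, is approximately

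f × √(1 − r²), with f = √[(N − 3)/(N − 4)] × t(N − 3)/t(N − 2).

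- N = 12: f = √(9/8) × 2.262/2.228 = 1.077.
- N = 24: f = √(21/20) × 2.080/2.074 = 1.028.

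| r | √(1 − r²) | N = 12, formula | N = 12, simulated | N = 24, formula | N = 24, simulated |
|---|---|---|---|---|---|
| 0.3 | 0.954 | 1.03 | 1.02 | 0.98 | 0.98 |
| 0.5 | 0.866 | 0.93 | 0.93 | 0.89 | 0.89 |
| 0.7 | 0.714 | 0.77 | 0.77 | 0.73 | 0.73 |
| 0.8 | 0.600 | 0.65 | 0.64 | 0.62 | 0.62 |

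The simulated columns come from 20,000 trials per cell on Gaussian clinic means. Bias was at most 0.007 between-clinic SD in both models. The break-even correlation is √(1 − 1/f²): 0.37 with 12 clinics (0.36 when simulated) and 0.23 with 24.

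**Step 2: the effect on power.** With 24 clinics, r = 0.5 and an effect of 0.5 SD, simulated power rises from 21.1% to 25.8%. At 0.8 SD it rises from 46.8% to 56.2%. With 12 clinics and r = 0.3 there is no gain.

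**Step 3: if Aim 2 inherits PIM level instead.** Let c be the correlation of pre-period PIM level with the outcome's own pre-period level. If PIM predicts the outcome only through that level, r is replaced by c × r, and the ratio is f × √(1 − c²r²). For r from 0.5 to 0.8:

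| | N = 12, simulated | N = 24, simulated |
|---|---|---|
| c = 0 | 1.07 | 1.03 |
| c = 0.3 | 1.04 to 1.06 | 1.00 to 1.02 |
| c = 0.6 | 0.94 to 1.02 | 0.90 to 0.98 |
| own level | 0.64 to 0.93 | 0.62 to 0.89 |

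A component of the primary outcome could have a higher c. With c = 0.9 and r = 0.8, c × r = 0.72 and √(1 − 0.518) = 0.694. The ratio is then 1.077 × 0.694 = 0.75 with 12 clinics and 1.028 × 0.694 = 0.71 with 24. That is much of the gain, but not all of it.

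**Step 4: the standard error.** The plan does not state which standard error the GEE uses. In the clinic-mean simulations, the type I error of an uncorrected sandwich z-test was:

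- 12 clinics: 10.3–10.7% without the covariate, 12.9–13.6% with it.
- 24 clinics: 7.1–7.7% without, 8.0–8.6% with.

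A Kauermann-Carroll correction with a t reference gave 4.7–5.9%. An exchangeable GEE on six monthly values (months 13 to 18; 1,000 runs per cell) gave similar uncorrected figures with 12 clinics: 10.1–13.0% without and 12.8–14.9% with. In that check, Mancl-DeRouen with t was conservative (2.6–5.1%). Its width ratios at r = 0.3, 0.5 and 0.7 were 1.10, 0.98 and 0.83 with 12 clinics. No log-link mixed model was simulated, so these error rates do not apply to the count outcome.

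**The case against.** The strongest reply is that the randomized comparison is valid without any baseline term, so this is a choice about efficiency and not an error. That is correct.

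A second reply is that the text may already cover the point. If the primary model adjusts for the pre-period level of its own outcome, a similar Aim 2 model would naturally adjust for the pre-period level of the Aim 2 outcome. This reading is fair, but the text does not settle it.

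A third is that many Aim 2 outcomes are parts of the PIM measure: PPIs, aspirin, CNS-active or anticholinergic drugs, the flagged-medication count, and the DOAC flag sub-components. For these, an inherited PIM term may already recover part of the gain. This also stands, and it narrows the concern mainly to costs, pharmacist reviews and any CBTI receipt.

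A fourth is that the data may not exist. Data from baseline are stated only for the primary outcome. Table 1 takes CBTI receipt from therapists' note templates. The 12-month look-back in the insomnia outcome implies earlier CBTI data, but their coverage is not described. This limits the fix to outcomes with usable pre-period data.

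A reader might go further and infer that the Aim 2 results are biased, or that the sponsor did leave the baseline out. The documents support neither. Randomization protects the unadjusted contrast, and silence about a term does not show that it was absent. Nor does an outcome title such as "Change in Mean Cognitive Behavioral Therapy for Insomnia (CBTI) Sessions Completed" settle the matter the other way: no change-score model is described, and that outcome could not be analysed.

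**Conclusion.** The point holds as a cheap improvement together with a gap in specification. No named Aim 2 model contains the pre-period level of its own outcome, and it is unstated whether the pre-period PIM term carries over.

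The size for this trial cannot be fixed. Under the assumed inputs it runs from a slight loss (about 2% wider with 12 clinics at correlation 0.3) to an interval 36% narrower with 12 clinics, or 38% narrower with 24, at correlation 0.8. A gain is likely where the correlation is about 0.5 or more. These figures rest on Gaussian clinic means, equal weights and 1:1 allocation, and carry over to the log-link count model only in direction.

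It would also be too strong to infer that the trial's type I error is inflated. The plan does not state the type of standard error, so that risk is conditional. It is a reason to pair the covariate with a corrected standard error, not a finding about the results.

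**What to change.** 1. State, for each Aim 2 outcome, whether the model carries its own pre-period level, the pre-period PIM level, or neither.
2. Wherever pre-period data exist, add the clinic's pre-period mean of that same outcome, over the same stated window as for PIM level. Use the log scale in the count model. For any CBTI receipt, check note-template coverage in the pre-period first.
3. In the GEE models only, use a small-sample-corrected standard error, such as Kauermann-Carroll, with a t reference on clinics minus clinic-level parameters.
4. The cover note describes the analysis in the past tense. Where an Aim 2 analysis is complete, report the adjusted model as a post hoc supplement, not a replacement.

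The cost is one degree of freedom per model and a pre-period extract per outcome, mostly from the administrative data already in use. In the least favourable case tabulated for an own pre-period level (12 clinics, correlation 0.3), the interval becomes about 2% wider with a t-based or Kauermann-Carroll interval, and about 10% wider with Mancl-DeRouen. The choice of correction should therefore be stated too.
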